8.2 FLOW CHART

A flow diagram will be performed according to ICHE3 and the consort statement in order to summarize the number of patients at study losses by time at each stage. Patients screened, eligible, consented, randomized, receiving their allocated treatment, withdrawing/lost to follow up, and included in the population set defined in the section 8.1.

8.3 ENDPOINTS DEFINITION

8.3.1 Primary outcomes

The primary outcomes are related to safety assessment as follow:

- Rate of adverse events (AE) with Common Terminology Criteria for Adverse Events (CTCAE) ≥ 3 excluding palmar-plantar erythrodysthesia, rate of AEs, rate of related-AEs and rate of death. Rate of AEs leading to treatment discontinuation.
- Adverse events will be graded following version 5.0 of the CTCAE of the National Cancer Institute, during treatment and 30 days after the last dose.

8.3.2 Secondary outcomes

ORR will be the first relevant ranked secondary outcome:

- Defined as a partial or complete response at any time, i.e. the best response from inclusion along all follow-up.

The rest of secondary end points are:

1. Time to progression (TTP): time to the first progression, defined as the time from the inclusion date to progression (i.e. date of progression event or censoring – date of inclusion + 1).
2. Pattern of progression:
 - Intrahepatic growth (IHG): increased size of intrahepatic target lesions or progression of intrahepatic "non-target" lesions at baseline.
 - New intrahepatic lesion (NIH): emergence of new intrahepatic lesions
 - Extrahepatic growth (EHG): increased size of extrahepatic target lesions, progression of extrahepatic "non-target" lesions at baseline or progression of the existing vascular invasion.
3. Rate of patients who develop new extra-hepatic spread

4. Overall survival (OS): defined as the time from the inclusion date to death from any cause (i.e. date of death event or censoring – date of inclusion + 1).
5. Post-progression survival (PPS), for those patients who progressed, the time from the progression date to death from any cause (i.e. date of death event or censoring – date of 1st progression + 1).

Please see description of the censoring rules for time to event variables in section 8.5.1.

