6.1.6 PERMANENT DISCONTINUATION OF CABOZANTINIB DUE TO ADVERSE EVENTS

Cabozantinib administration should be discontinued if at least one of the following drug-related adverse event(s) occurs:

- Subject no longer experiences clinical benefit as determined by the investigator. If study treatment is withdrawn for this reason, the date of this decision is to be recorded and every effort should be made to continue safety evaluations and collection of subsequent treatment information and follow-up information for survival.
- Unacceptable side effects the investigator feels may be due to study treatment, including any subject with a GI or non-GI perforation/fistula
- Any adverse event, laboratory abnormality or intercurrent illness, which, in the judgment of the Investigator, presents a substantial clinical risk to the subject with continuing study medication.
- Any Grade 3 non-skin, drug-related adverse event lasting $>$ 21 days
Exception of grade 3 drug-related AE:
 - Grade 3 drug-related laboratory abnormalities do not require treatment discontinuation except:
- Any drug-related Grade 4 drug-related adverse event or laboratory abnormality, except for the following events which do not require discontinuation:
 - Grade 4 neutropenia $<$ 7 days;

- Grade 4 lymphopenia or leukopenia;
- Grade 4 amylase or lipase abnormalities that are not associated with symptoms or clinical manifestations of pancreatitis;
- Isolated Grade 4 electrolyte imbalances/abnormalities that are not associated with clinical sequelae and are corrected with supplementation/appropriate management within 72 hours of their onset;
- The investigator feels it is not in the best interest of the subject to continue on study
- Participation in another clinical study using an investigational agent or investigational medical device
- Necessity for treatment with non-protocol systemic anticancer therapy
- Receipt of liver-directed local anti-cancer therapy (eg, transarterial tumor embolization or chemoembolization, radiofrequency or microwave ablation, percutaneous ethanol or acetic acid ablation, injection or infusion of drug eluting or radiation-emitting beads, cryoablation, radiation therapy, including stereotactic radiotherapy, or surgery)
- Necessity for withholding study drug for greater than 8 weeks for AEs, unless continuation of treatment is approved by the Principal Investigator

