| Study procedures and examinations | | | | | | | |
| Physical examination | x | x | x | * | x | x | |
| ECOG performance status | x | x | x | * | x | x | |
| 12-lead ECG ⁴ | x | | | | | x | |
| Vital signs ⁵ | x | x | x | * | x | x | |
| Assessment of AEs/SAEs | x | x | x | * | x | x | |
| Concomitant medications | x | x | x | * | x | x | |
| Diet and gut microbiota | x | | | | | | |
| | | | | | | | |
| Laboratory tests | | | | | | | |
| Serum chemistry ⁶ | x | x | x | * | x | x | |
| Hematology ⁷ | x | x | x | * | x | x | |
| Coagulation (PT, INR, PTT) | x | x | x | * | x | x | |
| HBsAg and HBsAb, HBcAb and HCV Ab; HBeAg and HBeAb, HBV DNA and HDV RNA and HDV Ab(HBV+ subjects only); HCV RNA (HCV+ subjects only) | x | | | | | x | |
| Thyroid function tests (TSH, free T3, free T4) | x | | | | | | |
| Urinalysis | x | x | x | * | | x | |
| Urine or serum pregnancy test (WOCBP) | x | | | | | | |
| | | | | | | | |
| Other procedures⁸ | | | | | | | |
| Other laboratory blood tests and assays ⁹ | | x | x Only in C1 | | x | | |
| Other liver tissue analysis ¹⁰ | x | | | * | x | | |
| Patient-reported Quality of Life (EQ-5D, EORTC-QLQ C30, EORTC-HCC18 and FACT-Hep) ¹¹ | | x | | | x | x | |
| Other stool tests and assays ¹² Day 1 | | x | | | | x | |

Sponsor's code: ACTION
EudraCT No: 2019-004991-20
Version: 4.0
Date: 15 July 2021
CONFIDENTIAL

Cycle 4 and in case of OR or PD

EOT: End of Treatment; **OR:** Objective Response; **PD:** Progressive Disease

¹ The time period between study entry and the commencement of protocol treatment is not to exceed 28 days.

² Follow-up visits could be on-site or phone visits after the last visit and will include survival data and liver cirrhosis complications evaluation every 3 months. If the patient does not start any other treatment after end of treatment, radiologic follow-up with the same scheduled will be preferred. Laboratory tests will be performed at the discretion of the treating investigator until death or the end of the study.

³ A biopsy will be performed at the time of progression whenever possible.

⁴ Note: The ECG should be performed within the 7 days prior the randomization. If the QTcF is > 500 ms in first ECG, a total of 3 ECGs should be performed. If the average of these 3 consecutive results for QTcF is ≤ 500 ms, the subject meets eligibility in this regard.

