Target Lesions: All measurable lesions up to a maximum of 2 lesions per organ and 5 lesions in total, representative of all involved organs should be identified as *target lesions* and be recorded and measured at baseline. These 5 lesions should be selected on the basis of their size (lesion with the longest diameter), be representative of all involved organs and should be suitable for reproducible repeated measurements. A sum of the diameters (longest for non-nodal lesions, short axis for nodal lesions) for *all target lesions* will be calculated and reported as the baseline

sum diameters. If lymph nodes are to be included in the sum, then as noted above, only the short axis is added into the sum. The baseline sum diameters will be used as reference to further characterize any objective tumor regression of the measurable dimension of the disease. If there are >5 measurable lesions, those not selected as *target lesions* will be considered together with non-measurable disease as *non-target lesions*.

Non-target Lesions: All non-measurable lesions (or sites of disease) plus any measurable lesions over and above the 5 listed as *target lesions*. including pathological lymph nodes (with short axis ≥ 10 mm and < 15 mm) should be identified as non-target lesions and should also be recorded at baseline. Measurements are not required but these lesions should be noted at baseline and should be followed as "present", "absent" or in rare cases "unequivocal progression". In addition, it is possible to record multiple non-target lesions involving the same organ as a single item on the case record form (eg; 'multiple enlarged pelvic lymph nodes' or 'multiple liver metastases').

Best Response

The best overall response is the best response recorded from the start of the study treatment until the end of treatment. The patient's best overall response assignment will depend on the findings of both target and non-target disease and will also take into consideration the appearance of new lesions. While some non- target lesions may actually be measurable, they need not be measured and instead should be assessed only qualitatively at the time points specified in the protocol.

All subjects will have their BEST RESPONSE on study classified as outlined below:

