8.5 STUDY ESTIMAND, HANDLING OF MISSING DATA AND CENSORING RULES

The handling of missing data will follow the principles specified in the ICH-E9 and the CPMP/EWP/1776/99 Rev1¹³. Guideline on Missing Data in confirmatory trials Guidelines. As per the ICH E9(R1) (Addendum on estimands and sensitivity analysis in clinical trials EMA/CHMP/ICH/436221/2017)¹⁴, the plan for the assessment of the Primary endpoint (PEP) (in this study includes the main secondary outcome) is described here after using the 4 attributes of the estimand:

1. Population: as described in protocol and section 8.1 of this SAP, all analyses will be carried out using Safety population.
2. Endpoints: (please see details on the endpoints definitions in section 8.3)
 - a. Non confirmatory primary endpoints (PEPs): the rate and type of:
 - Any AEs
 - Related-AEs
 - Rate of death
 - AEs leading to treatment discontinuation
 - Serious AEs (SAEs)
 - Rate of AEs (CTCAE)≥3 excluding palmar-plantar erythrodysthesia
 - b. Secondary endpoints (SEP):
 - ORR (main secondary outcome)
 - Overall survival (OS)
 - Time to progression (TTP)

- Pattern of progression
- Post-progression survival (PPS)
- Rate of patients who develop new extra-hepatic spread

3. **Intercurrent events (ICEs)**: the relevant intercurrent events expected to occur in this study includes the following situations and the method for handling will be the same for all of them due to the safety characteristics of the primary objective. The “Treatment Policy” strategy will be used, i.e., all observed data will be used regardless of the intercurrent event.

- a. No treatment initiation: exclusion from the analysis.
- b. Main estimand: any other situation regardless of the ICE (use of rescue medication, prohibited concomitant medication, treatment discontinuation, or any reason leading to study discontinuation): “Treatment Policy” strategy (i.e. all observed data will be considered regardless of any previous ICE).
- c. Supplementary estimand: for some relevant efficacy secondary endpoints, data after ICEs will be censored (see table below) and will be based on the while on treatment strategy.

4. **Population-level summary**:

- a. Estimation of rates and 95%CI for the PEPs by means of Clopper-Pearson exact method will be used as the population-level summary (see sections 8.6.5.1 and 8.6.5.2.1).
- b. Time to event variables will be described using the Kaplan-Meier method (see section 8.6.5.2.2).

	Primary Estimand	Supplementary Estimand

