Primary endpoints		
Any AEs Related-AEs Rate of death AEs leading to treatment discontinuation Serious AEs (SAEs) Rate of AEs (CTCAE)≥3 excluding palmar-plantar erythrodysthesia	Treatment policy	None
Secondary endpoints		
ORR (main secondary outcome)	Treatment policy	While on treatment*
Overall survival (OS)		
Time to progression (TTP)		
Pattern of progression	Treatment policy	None
Rate of patients who develop new extra-hepatic spread		
Post-progression survival (PPS)		

*(censored after treatment ICEs)

The ORR rate will be handled using the Treatment Policy strategy. In the unexpected case of missing due to no radiologic assessment was conducted, the composite strategy will be applied by imputing to ORR to failure.

No formal imputations will be performed for any other variable. For the categorical variables the analyses will be based on the Available Data Only (ADO) approach. With regards to the continuous variables, mixed models^{15,16,17} are robust to the presence of missing at random (MAR) and conducts the analysis with all participants despite the presence of missingness. Of note, this method calculates the estimations based on the variance-covariance structure but without any formal imputations.

No formal imputation will be used for dates due to all post-inclusion dates are complete date.

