8.5.1 Censoring rules

TPP:

- Death without progression will be censored at the time of the last adequate radiological tumor assessment.
- Progression documented between scheduled assessments: Event at date of adequate radiological tumor assessment
- If a patient has not progressed at the time of database cutoff, the TPP of this patient will be censored at the last adequate tumor assessment before the database cutoff.
- Documented progression or death after missing ≥ 2 consecutive post-baseline tumor assessments: date of last adequate tumor assessment before missed assessments or date of inclusion, whichever is later.
- Patient lost to follow-up (or withdrew consent from study participation) before documented progression: date of last adequate tumor assessment.
- Please see comment below on the “treatment policy” and “while on treatment” estimands

Overall survival (OS):

- If a patient is alive at the time of last contact before the database cutoff, the OS of this patient will be censored at the date of last contact.
- Patient lost to follow-up (or withdrew consent from study participation) before death: date of last documented alive information
- Please see comment below on the “treatment policy” and “while on treatment” estimands

Post-progression survival (PPS)

- Same rules as OS

Handling of “treatment policy” and “while on treatment” estimands: If a patient discontinues study treatment or any other ICE is recorded before any event is documented, data from this patient will not be censored for the primary estimand (treatment policy). However, data will be censored for the supplementary estimand (while on treatment) at the last tumor assessment before the discontinuation of study treatment.

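### The SAP's main ORR runs past the end of treatment, where the protocol's best-response window stops, so it can count a response first seen under a later therapy

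*SAP*

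**What the plan says.** **Rank and definition.** SAP 8.3.2 states: "ORR will be the first relevant ranked secondary outcome". It then gives the definition: "Defined as a partial or complete response at any time, i.e. the best response from inclusion along all follow-up".

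**Main analysis.** SAP 8.5 states: "The ORR rate will be handled using the Treatment Policy strategy". It explains that strategy to mean that "all observed data will be considered regardless of any previous ICE". The intercurrent events it names include treatment discontinuation and prohibited concomitant medication.

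**Supplementary analysis.** The estimand table in SAP 8.5 lists a while-on-treatment version for ORR. Under SAP 8.5.1, "data will be censored for the supplementary estimand (while on treatment) at the last tumor assessment before the discontinuation of study treatment".

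**Protocol window.** Appendix 3 (section 14.3), which sets out RECIST 1.1 for this trial, states: "The best overall response is the best response recorded from the start of the study treatment until the end of treatment". SAP 6.2 also names RECIST 1.1 as the response standard.

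**After treatment.** Protocol 6.1.6 lists, among the reasons for stopping cabozantinib permanently, "Necessity for treatment with non-protocol systemic anticancer therapy", and separately the receipt of liver-directed local treatment. On imaging, footnote 2 to protocol Table 5 states: "If the patient does not start any other treatment after end of treatment, radiologic follow-up with the same scheduled will be preferred". The SAP 7.7 flow chart repeats that footnote.

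**The concern.** The two documents close the response window at different times. Because another systemic therapy or liver-directed treatment is a ground for stopping cabozantinib, the protocol's cut at end of treatment largely keeps the effects of those treatments out of ORR. The SAP removes that cut from its main analysis and puts no other in its place.

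SAP 8.5 justifies the common treatment-policy approach by the safety nature of the primary objective. That reasoning does not carry over to tumour response in a single-arm trial. No control group receives the same later therapies, so a response under one of them would be read as cabozantinib activity. Protocol 9.1 plans indirect comparison with external data through the 95% confidence intervals, so the ORR will be interpreted even though it is secondary.

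**Working it through.** Neither document gives a target, power or expected count for ORR, so there is no planned figure to reproduce. The check is a comparison of the texts, followed by an illustration of scale.

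**1. The windows side by side**

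| | Protocol Appendix 3 | SAP main ORR (8.3.2, 8.5) | SAP supplementary ORR (8.5, 8.5.1) |
|---|---|---|---|
| Opens | Start of study treatment | Inclusion | Not restated for ORR |
| Closes | End of treatment | End of all follow-up | Last tumour assessment before discontinuation |
| Explicit cut at a new anticancer therapy | No, but such therapy is a ground for ending treatment (6.1.6) | No | No, but data after discontinuation are excluded |
| Explicit cut at progression | No | No | No |

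The difference at the opening should not affect ORR, because SAP 8.6.3 takes as baseline the last measurement before the first administration. The difference at the close does matter.

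**2. Who is exposed.** The main ORR changes only for a patient who (a) has no response on cabozantinib, (b) stops it, (c) starts another therapy, (d) is scanned after that, and (e) then meets the Appendix 3 criteria. Step (d) is not scheduled: the Table 5 footnote prefers continued imaging only where no other treatment is started. Under step (e), a partial response needs at least a 30% decrease from the baseline sum of diameters, no new lesions and no unequivocal non-target progression. Many patients who progressed on cabozantinib would fail (e). The most exposed are those who stop without progression, for example for toxicity, and go on to another therapy.

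**3. Illustration of scale.** Inputs: n = 40 (protocol synopsis); the Clopper-Pearson 95% CI (protocol 9.1, SAP 8.6.2); and the 4% ORR that protocol 1.2.3 quotes for cabozantinib in the phase 3 trial, used only to choose a starting point. The number of late responses is an assumption, taken from 0 to 3.

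- Expected responders at 4%: 40 × 0.04 = 1.6, so start from 2.
- Effect of one added responder: 1/40 = 2.5 percentage points.
- With x responders, the lower limit is the 0.025 quantile of Beta(x, 41 − x) and the upper limit the 0.975 quantile of Beta(x + 1, 40 − x).

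| Late responses counted (assumed) | Responders | ORR | 95% CI |
|---|---|---|---|
| 0 | 2/40 | 5.0% | 0.6 to 16.9 |
| 1 | 3/40 | 7.5% | 1.6 to 20.4 |
| 2 | 4/40 | 10.0% | 2.8 to 23.7 |
| 3 | 5/40 | 12.5% | 4.2 to 26.8 |

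One late response raises the estimate by half (7.5/5.0 = 1.5), though the intervals for 2/40 and 3/40 overlap almost entirely. Only the extreme case of three moves the lower limit above 4%.

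**The case against.** The strongest reply is that the SAP already holds the analysis being asked for. Its while-on-treatment ORR drops everything after discontinuation, treatment policy is a declared estimand choice, and the request amounts to exchanging two labels. Much of this stands, and a reader should not infer that the SAP has no analysis free of later therapies. But the version closest to the protocol's definition is the supplementary one, and the SAP gives no reason specific to response for departing from Appendix 3. The supplementary rule is also written as censoring, for time-to-event outcomes. SAP 8.6.5.2.1, which covers binary outcomes, and Table 10 specify no separate while-on-treatment ORR.

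A second reply is that follow-up may mean only the scheduled on-treatment visits, since the protocol synopsis uses the word that way. The wording allows this, but the treatment-policy rule of using all data after discontinuation favours the wider reading. The ambiguity is itself a reason to fix the text.

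A third reply is that the exposure is small and ORR is secondary. This stands. SAP 8.6 describes the analyses as non-inferential, and the primary safety outcome, sample size and stopping rule are untouched. A reader might infer that the ORR will be inflated, or that the two documents must give different results. The texts support only that they could differ, and only if a first response appears after treatment ends. The 4% reference comes from sorafenib-treated patients, a different population, and serves here only for scale.

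**Conclusion.** The point holds in this limited form. The protocol and SAP define the window for the first-ranked secondary outcome differently, and the SAP's main version can count a response first seen after cabozantinib has stopped and another systemic or liver-directed therapy has begun. Each such response would add 2.5 points at n=40. How many would occur cannot be known from the documents; the range of 0 to 3 is assumed, and the absence of scheduled scans together with the response criteria points to the low end.

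Two further inferences should be avoided. Appendix 3 does not end best response at progression or at the start of new therapy: its stated limit is end of treatment, and protocol 6.1.7.1 allows treatment beyond progression. Nor do the documents show that start dates of later therapy are available: Listing 33 is titled only as subsequent treatments, and SAP 8.4.2 does not name them as a variable. The wording conflict is certain; the size of any bias is not.

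**What to change.** 1. In SAP 8.3.2 and 8.5, define the main ORR as the best RECIST 1.1 response from first dose until end of treatment, matching Appendix 3, and exclude any assessment after the start of another anticancer therapy.
2. Report the all-follow-up (treatment-policy) ORR as supplementary, and show both versions in Table 10.
3. State whether response is also cut at first progression. This is a separate choice for the sponsor, because Appendix 3's best-response window has no such cut and treatment beyond progression is allowed.
4. Confirm that the case report form captures start dates for subsequent systemic and liver-directed therapy.

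The cost is SAP wording and, if the dates are captured, a date filter in the ORR derivation. ORR may come out slightly lower. Responses first seen after treatment ends without any new therapy, which may well be due to cabozantinib, would appear only in the supplementary analysis.

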8.4 VARIABLES

8.4.1 Demographic characteristics, screening and baseline

The following pre-treatment characteristics (only recruited pre-treatment) will be analysed:

- Informed consent
- Demographic data and vital signs
- Clinical characteristics at HCC diagnosis
- Clinical characteristics at study entry
- Comorbidities
- First line treatment
- Selection criteria

